8.6. Data Analysis

Analyses will be based on patients receiving rimegepant or triptans only as an acute treatment currently for their migraine.

Data will be stratified by time spent on rimegepant or triptans and number of migraine related headache days.

Analysis will be descriptive. The mean, standard deviation (SD), median, 25th and 75th percentiles and minimum and maximum values will be reported for numeric variables, whilst relative frequencies and percentages will be reported for categorical variables.

The real-world nature of the DSP means many variables will contain missing data. We would expect the base of patients to vary from variable to variable due to imperfect physician knowledge, physicians not wishing to answer the question, etc. The base relevant to each analysis will be reported in any data tables provided. There will be no imputation of missing data. Where missing values are found in a particular variable, any patients with missing values will be removed from all pieces of analysis where that variable is used. However, patients removed from one piece of analysis are still eligible for inclusion in other analyses. In the derivation of PRO variables, the handling of missing data will follow the official instructions as provided by the author/owner of the PRO questionnaire.

Detailed methodology for summary and statistical analyses of data collected in this study is documented in a statistical analysis plan (SAP) below:

8.6.1. Analysis Plan for Describing Patients with Migraine Receiving Rimegepant or Triptans PRN

Variable	Data Source(s)	Analysis Plan
Patient age	PRF AQ1	Mean, Median, SD, Q1, Q3, Min, Max to be displayed
Patient biological sex	PRF AQ2	Proportion of responses to: Male, Female, Intersex
Patient BMI	PRF AQ3/4	Mean, Median, SD, Q1, Q3, Min, Max to be displayed
Patient ethnicity	PRF AQ6	Proportion of responses to: White / African American / Native American / Asian (Indian subcontinent) / South-East Asian / Asian (other) / Hispanic / Middle Eastern / Other
Employment status	PRF AQ8	Proportion of responses to: Working full time / Working part-time / Retirement / Student / Unemployed / Long-term sick / Home maker Responses of “Don’t know” will be omitted from analysis.
	PRF AQ9	Proportion of responses to: Yes / No Responses of “Don’t know” will be omitted from analysis.
	PRF AQ10	Number of days taken off work/studies in last 3 months due to migraine presented as Mean, Median, SD, Q1, Q3, Min, Max to be displayed. Responses of “Don’t know” will be omitted from analysis.
Insurance type	PRF AQ14	Proportion of responses to: Medicaid / Medicare / Commercial / Exchange plan / Cobra / Non-medicare retired benefit /

Variable	Data Source(s)	Analysis Plan
		Tricare/veterans / Other / No insurance Responses of “Don’t know” will be omitted from analysis.
Migraine diagnosis-chronic?	PRF CQ5	Proportion of responses to: Yes / No
Number of migraine related headache days in last 3 months	PRF CQ4bi	Mean, Median, SD, Q1, Q3, Min, Max to be displayed
Severity of attacks over last 3 months	PRF CQ7a	Proportion of responses to: Very mild / Mild / Moderate / Severe / Very Severe
Current migraine symptoms	PRF CQ6a	Proportion of responses to: Pain on one side of the head / Pain that moves from one side of the head to another/ Pain on both sides of the head at the same time / Pulsating/throbbing pain / Pain worsened by activity / Photophobia / Sensitivity to smell / Visual aura / Light-headedness / Speech changes / Sensory aura / Nausea / Vomiting / Allodynia / Watery/swollen/red eyes / Facial swelling / Runny nose/nasal congestion / Ear congestion / Kinesiophobia / Muscle weakness / Mood changes / Changes in appetite / Other / Unknown Responses of “Don’t know” will be omitted from analysis.
Most bothersome migraine symptoms	PRF CQ6b	Proportion of responses to: Pain on one side of the head / Pain that moves from one side of the head to another/ Pain on both sides of the head at the same time / Pulsating/throbbing pain / Pain worsened by activity / Photophobia / Sensitivity to smell / Visual aura / Light-headedness / Speech changes / Sensory aura / Nausea / Vomiting / Allodynia / Watery/swollen/red eyes / Facial swelling / Runny nose/nasal congestion / Ear congestion / Kinesiophobia / Muscle weakness / Mood changes / Changes in appetite / Other / Unknown Responses of “Don’t know” will be omitted from analysis.
Duration of attack without acute treatment (hours or days)	PRF CQ10	Mean, Median, SD, Q1, Q3, Min, Max to be displayed. Responses will be calculated into one unit of choice- hours or days. Responses of “Don’t know” will be omitted from analysis.
Other headache conditions	PRF CQ3	Proportion of responses to: Tension type headache / Medication overuse headache / Cluster headache / SUNCT / Hemicrania continua / New daily persistent headache / Primary stabbing headache / Primary exercise headache /

Variable	Data Source(s)	Analysis Plan
Current comorbidities	PRF KQ2/LQ1	
Primary thunderclap headache / Hypnic headache / Secondary headaches / Other headache conditions / None
 
Responses of “None” will be omitted from analysis.
 
Proportion of responses to: Myocardial infarction / Ischaemic stroke / Haemorrhagic stroke / TIA / Cerebrovascular disease / Hypertension / Hypotension / Ischaemic heart disease / Congestive heart failure / Atrial fibrillation / Arrhythmia / Angina / Deep vein thrombosis / Cardiomyopathy / Coronary artery disease / Peripheral vascular disease / Mitral valve disease / Reynaud’s disease / Type 1 diabetes (with and without complications) / Type 2 diabetes (with and without complications) / Obesity / Thyroid disease / Hyperlipidaemia / Dyslipidaemia / Mild/Moderate/Severe renal disease / Mild/Moderate/Severe liver disease / NASH/ Depression / Anxiety / Stress / Vascular dementia / Alzheimer’s disease / Other dementia / Epilepsy / Parkinson’s disease / Obsessive compulsive disorder / Panic disorder / Sleeping disorders / Seizures / Vertigo / Chronic pulmonary disease / Asthma / Chronic sinusitis / Connective tissue disease / Hemiplegia/Paraplegia / Rheumatologic disease / Arthritis / Neuropathic pain / Osteoporosis / Neck pain / Back pain / Fibromyalgia / Trigeminal neuralgia / Muscle weakness / Any malignancy / Metastatic solid tumour / Tumour without metastases / Gastrointestinal problems / Peptic ulcer disease / Lupus / Anorexia / Alcoholism / Menstrual disorders / IBS / Glaucoma / AIDS/HIV / Erectile dysfunction / Long term effects of COVID-19 / Other / None
 
Responses of “None” will be omitted from analysis.

Patient receiving acute treatment(s) previously	PRF DQ10	
Proportion of responses to: Triptan(s) including combinations / NSAID(s) including combinations / Anti-CGRP gepants / Opioid analgesics including combinations / Non-opioid analgesics including combinations / Ergotamines and Derivatives / Serotonin 5-HT1F agonist (ditan) / Other / No drug treatment
 
Responses of “No treatment” will be omitted from analysis.
 
Responses of ‘Triptan’ and ‘Triptan combinations’ will be combined.

Time spent on Rimegepant or triptans (currently)	PRF DQ2a	Mean, Median, SD, Q1, Q3, Min, Max to be displayed. Responses will be calculated into one unit of choice- days,

Variable	Data Source(s)	Analysis Plan
receiving)		weeks or months. Responses of “Don’t know” will be omitted from analysis.
Patient current preventive treatment(s)	PRF EQ1	Proportion of responses to: Yes / No, but this patient has received preventive prescribed treatment(s) for their migraine in the past / No, and this patient has never received prescribed preventive treatment(s) for their migraine
Patient receiving preventive treatment(s) previously	PRF EQ3 PRF EQ10	Proportion of responses to: Anti-CGRP mAbs, Anticonvulsants, Beta-blockers, Anti-CGRP gepant, Antidepressant/Anxiolytics/Benzodiazepines / Calcium antagonists / Contraceptive / NSAIDs (including combinations), Opioid analgesics (including combinations) Neurotoxins / Other / No drug treatment Responses of ‘No treatment’ will be omitted from analysis. Responses of ‘Rimegepant’ will be omitted from analysis. Proportion of responses to: Anti-CGRP mAbs, Anticonvulsants, Beta-blockers, Anti-CGRP gepant, Antidepressant/Anxiolytics/Benzodiazepines / Calcium antagonists / Contraceptive / NSAIDs (including combinations), Opioid analgesics (including combinations) Neurotoxins / Other / No drug treatment Responses of ‘No treatment’ will be omitted from analysis.

8.6.2. Analysis Plan for Objective 1

Objective 1 focuses on the reliability of effect of rimegepant or triptans over multiple attacks when taken PRN to treat migraine. This will be addressed by describing the following:

Variable	Data Source(s)	Analysis Plan
Failure to achieve pain freedom within 2 hours post dose (physician perspective)	PRF DQ18	Proportion of responses to: Yes / No Responses of “Don’t know” will be omitted from analysis.
Reason for choice of current acute treatment- ‘consistency of response after repeated use’ (physician perspective)	PRF FQ1a	Proportion of responses to: Complete pain freedom after 2 hours / Pain relief after 2 hours / Relieves most bothersome migraine symptom / Fast onset of action / Relieves even the most severe migraine attacks / Prolonged pain relief/long duration of action / Avoids the need for a second dose or rescue treatment / Low headache recurrence (within 24 hours of attack) / Tends to work across all patients / Consistency of response after repeated use / Dual use treatment- a single drug to achieve acute and preventive treatment effects / Ability to prescribe a stronger initial dose, rather than multiple additional doses / Ability to take additional doses for non/partial response / Available as a table/capsule / Available as a melt / Available as a patch / Available via nasal administration / Available as an injection / Ability to prescribe for consecutive days (eg, for menstrual migraine and other trigger events) / Allows rapid return to function / Patient can continue activities and honour commitments / Patient can enjoy recreational/leisure activities / Reduces number of days missed from school/work / Improves patient’s quality of sleep / Patient can maintain relationships / Low risk of medication overuse headaches with repeated use / Lower risk of paraesthesia (abnormal sensation(s) of the skin) / Lower risk of palpitations/flushing / Lower risk of other CV side effects / Lower risk of nausea/vomiting / Lower risk of other GI side effects / Lower risk of memory/concentration problems / Lower risk of drowsiness/sedation / Lower risk of dizziness / Lower risk of fatigue / Lower risk of liver damage / Lower risk of weight problems / Lower risk of depression / Lower risk of allergic reaction / Lower risk of breathing difficulties / Lower/no risk of injection site reaction / Lower risk of addiction/abuse / Suitable for adjunctive/add-on therapy / Lack of interaction with other drugs / Safe for long term use / Efficacious in patients who have failed prior acute migraine treatments / Suitable for patients with moderate/high CV risk / Safe in patients with cardiac/circulatory disorders / Suitable for vomiting/nauseous patients / Suitable for patients with menstrual migraine / Suitable for women of child bearing age / Suitable for women of child bearing age / Suitable for physically active patients / Suitable for use in career orientated professionals / Approved for migraine / Good patient adherence / Patient convenience / Patient request/preference for therapy / Cost effective treatment / Persona; experience prescribing this

PFIZER CONFIDENTIAL

CT24-WI-GL02-RF02 5.0 Non-Interventional Study Protocol Template For Secondary Data Collection Study

01-Aug-2023

Page 27 of 36

Variable	Data Source(s)	Analysis Plan
		drug / On local/national formulary / Clinical trial/publication evidence / Other selected for rimegepant or triptans
Number of migraine attacks acute treatment achieves pain freedom within 2 hours post dose (patient perspective)	PSC HQ6	
Proportion of responses to: 0 out of every 5 attacks / 1 out of every 5 attacks / 2 out of every 5 attacks / 3 out of every 5 attacks / 4 out of every 5 attacks / 5 out of every 5 attacks
 
Success will be defined as responses to '4 out of every 5 attacks' or '5 out of every 5 attacks' combined

8.6.3. Analysis for Objective 2

Objective 2 focuses on satisfaction of physicians and patients with rimegepant or triptans to treat migraine acutely. This will be addressed by describing the following:

Variable	Data Source(s)	Analysis Plan
Satisfaction with current acute treatment (physician perspective)	PRF IQ1a	
Proportion of responses to: Extremely satisfied / Satisfied / Slightly Satisfied / Neither satisfied nor dissatisfied / Slightly dissatisfied / Dissatisfied / Extremely dissatisfied
 
Satisfaction will be defined as responses to: 'Extremely satisfied' or 'Satisfied' or 'Slightly Satisfied' combined
 
Dissatisfaction will be defined as responses to: 'Neither satisfied nor dissatisfied' or 'Slightly dissatisfied' or 'Dissatisfied' or 'Extremely dissatisfied' combined
 
Data to be matched to PSC equivalent data (PSC HQ18a)

Drivers for lack of satisfaction with current acute treatment (physician perspective)	PRF IQ1b	Proportion of responses to: Lack of efficacy / Slow onset of action / Efficacy diminished over time / Number of side effects experienced / Severity of side effects experienced / Mode of administration / Complicated dosing regimen / The number of prescribed acute treatments / The treatment is costly for the patient / Other

Variable	Data Source(s)	Analysis Plan
Satisfaction with current acute treatment (patient perspective)	PSC HQ18a	
Proportion of responses to: Extremely satisfied / Satisfied / Slightly Satisfied / Neither satisfied nor dissatisfied / Slightly dissatisfied / Dissatisfied / Extremely dissatisfied
 
Satisfaction will be defined as responses to: 'Extremely satisfied' or 'Satisfied' or 'Slightly Satisfied' combined
 
Dissatisfaction will be defined as responses to: 'Neither satisfied nor dissatisfied' or 'Slightly dissatisfied' or 'Dissatisfied' or 'Extremely dissatisfied' combined
 
Data to be matched to PRF equivalent data (PRF IQ1a)

Drivers for lack of satisfaction with current acute treatment (patient perspective)	PSC HQ18b	
Proportion of responses to: It only reduces my migraine pain by half / It reduces my migraine pain by less than half / It does not work quickly enough / It does not work as well as it used to / The number of side effects I experience / The severity of the side effects I experience / I am not happy with the way I have to take it / I find it difficult to know when to take it / I have too many different acute treatments to take / I worry about becoming dependent on it / It costs me too much money / Other

8.6.4. Analysis for Objective 3

Objective 3 focuses on willingness of patients to continue taking rimegepant or triptans to treat their migraine attacks. This will be addressed by describing the following:

Variable	Data Source(s)	Analysis Plan
Patient willingness to continue use of acute treatment (patient perspective)	PSC HQ18c	
Proportion of responses to: Definitely yes / Probably yes / Do not know / Probably not / Definitely not
 
Responses of "Don't know" will be omitted from analysis.
 
Willingness to continue will be defined as responses to: 'Definitely yes' or 'Probably yes' combined
 
Unwillingness to continue will be defined as responses to 'Probably not' and 'Definitely not' combined

8.6.5. Analysis for Objective 4

Objective 4 focuses on the proportion of those treating acutely with rimegepant or triptans that are optimised on their treatment. This will be addressed by describing the following:

Variable	Data Source(s)	Analysis Plan
Migraine Treatment Optimization Questionnaire (m-TOQ6)	PSC Section I- m-TOQ6	Reported by proportion of responses per time item and total score. The official m-TOQ6 scoring algorithm will be used to calculate total score.
When patient takes acute treatment	PSC HQ3	Proportion of responses to: Before any sign of a migraine attack, but in anticipation of one starting / At the first sign of a migraine attack (before the pain starts) / When the pain starts / After the pain has started and I have an idea of how severe it is
Number of days per month patient takes acute treatment	PSC HQ4a	Mean, Median, SD, Q1, Q3, Min, Max to be displayed.

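### Section 8.6.1 omits the valid answers None and No treatment for other headache conditions, comorbidities and prior acute treatment, and leaves the denominator undefined

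*Combined protocol and SAP*

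**What the plan says.** Three rows of the table in section 8.6.1 are concerned, all taken from the physician's record form.

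- **CQ3, other headache conditions.** The row begins "Proportion of responses to: Tension type headache / Medication overuse headache / Cluster headache / SUNCT" and its list ends "Secondary headaches / Other headache conditions / None". None is therefore one of the answers whose proportion is to be reported.
- **KQ2/LQ1, comorbidities.** The list ends "Long term effects of COVID-19 / Other / None". For this item and for CQ3 the list is followed by "Responses of “None” will be omitted from analysis".
- **DQ10, prior acute treatment.** No drug treatment is a listed answer, and the rule is "Responses of “No treatment” will be omitted from analysis".

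The same sentence form is applied elsewhere in the table to Don't know, for example for employment and insurance. For insurance (AQ14) the negative answer, having no insurance, stays in the list and only Don't know is removed.

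Section 8.6 removes a patient from an analysis only where the variable is missing, and promises that each table will show its base. No denominator is stated for the three items.

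**The concern.** None is information: the physician has recorded that the patient has no such condition or has had no such drug. Don't know is the absence of information. Treating both with one sentence invites a programmer to treat both as missing. The plan also pulls two ways within a single cell, asking for the proportion answering None and then ordering it left out.

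Two tables can be produced from this text:

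- **Patient dropped (the literal reading).** Those answering None leave the base, so each percentage describes only patients with at least one condition or prior drug.
- **Row dropped.** Everyone who answered stays in the base and only the None line is not printed. The percentages are right, but the share of patients with no comorbidity, no other headache or no prior acute treatment is not reported.

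This matters because Amendment 1 brings in triptans for a descriptive comparison with rimegepant. The groups are not randomised and no adjustment is planned, so the characteristics tables are where a reader would look to see how alike the groups are. Section 8.9 also counts the full treatment history on the record form as a strength, and having had no earlier acute drug is part of that history.

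**Working it through.** **Inputs.** Section 8.5 gives the physician-reported sample as 528, made up of 91 rimegepant and 437 triptan patients; 91 + 437 = 528, so the base reproduces. The documents give neither the share answering None nor the prevalence of any condition. Those below are assumptions chosen to show the range.

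**Formulas.** Let N be the group size, x the number with a given condition and q the share answering None, with no other missing answers.

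- Row dropped: x/N.
- Patient dropped: x/(N − number answering None), which is x/N multiplied by 1/(1 − q).
- The triptan-to-rimegepant ratio of percentages is multiplied by (1 − qR)/(1 − qT), where qR and qT are the rimegepant and triptan shares.

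**Same share in both groups.** Take a condition in 18/91 = 19.8% and 87/437 = 19.9%. With only the row dropped, these figures stand at any q. With the patient dropped:

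| Assumed q (about) | Rimegepant: None, base, shown | Triptans: None, base, shown |
|---|---|---|
| 10% | 9, 82, 18/82 = 22.0% | 44, 393, 87/393 = 22.1% |
| 20% | 18, 73, 18/73 = 24.7% | 87, 350, 87/350 = 24.9% |
| 40% | 36, 55, 18/55 = 32.7% | 175, 262, 87/262 = 33.2% |
| 60% | 55, 36, 18/36 = 50.0% | 262, 175, 87/175 = 49.7% |

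The levels are inflated but the groups still look alike.

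**Different shares, patient dropped.**

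- *Imbalance created.* True figures are 14/91 = 15.4% and 66/437 = 15.1%. At q of 30% in both groups the table shows 14/64 = 21.9% and 66/306 = 21.6%. At 30% for rimegepant and 40% for triptans it shows 14/64 = 21.9% and 66/262 = 25.2%. The factor is 0.70/0.60 = 1.17.
- *Imbalance hidden.* True figures are 27/91 = 29.7% and 87/437 = 19.9%. At 10% and 40% the table shows 27/82 = 32.9% and 87/262 = 33.2%. The factor is 0.90/0.60 = 1.50.

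**Row dropped.** Neither distortion occurs. What is lost is q itself, for example 36/91 = 39.6%.

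**Does printing the base settle it?** Not fully. A rimegepant base of 55 fits 36 None and 0 missing, where the right figure among those who answered is 18/91 = 19.8%. It equally fits 0 None and 36 missing, where it is 18/55 = 32.7%. These are the two extremes; mixtures fall between them.

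**The case against.** The best defence is that only the row is meant to go. Section 8.6 removes patients for missing values only, None is not missing, and the rule speaks of responses, not patients. The table also edits categories elsewhere: "Responses of ‘Triptan’ and ‘Triptan combinations’ will be combined". In the preventive-treatment rows the same sentence is applied to a substantive answer: "Responses of ‘Rimegepant’ will be omitted from analysis". This makes row suppression a real alternative, but it does not settle the matter, because the identical wording for Don't know presumably does remove the patient. The sentence on rimegepant is weak support, since section 8.2.2 already excludes patients prescribed rimegepant for prevention and it may have nothing to act on among current preventives.

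Second, the base must be printed, so a shrunken denominator would be visible and a reader could recover the count. That stands in part. The three items list no Don't know option, which removes one source of uninformative answers. But section 8.6 expects gaps in many variables, and the base alone cannot separate None from a blank.

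Third, every None share above is assumed, and the hidden-imbalance example needs a 30-point gap between the groups. That is correct: the examples show what the rule permits, not what the data contain.

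Fourth, the reach is small. The study is descriptive, and age, sex, BMI, chronic status, headache days, attack severity and current preventive use (EQ1) are untouched, as are the Objective 1 to 4 outcomes and both stratifiers. This stands in full and limits the weight of the point.

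**Conclusion.** The concern holds. Section 8.6.1 orders a valid negative answer omitted for three items and does not define the resulting denominator. Taken literally, each percentage is multiplied by 1/(1 − q): about 1.25 at 20% None, 1.65 to 1.67 at 40% and 2.5 at 60%. Differing shares also distort the comparison between groups. On the milder reading nothing is inflated, but the share with none goes unreported, and these items have no separate unconditional split of the kind EQ1 provides for preventive treatment. Neither reading gives a complete description.

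The ambiguity and the omission rest on the text alone. The size rests on assumed None shares and on patients being dropped, which the documents do not confirm. It should be fixed, but no conclusion on a study objective depends on it.

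**What to change.** For CQ3, KQ2/LQ1 and DQ10, replace the omission sentence with a rule that None or No drug treatment is kept in the denominator and reported as its own row, that only missing or unknown answers are excluded, and that the denominator is the number of patients with an answer to the item.

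The prior-preventive rows (EQ3/EQ10) carry the same wording, "Responses of ‘No treatment’ will be omitted from analysis". Either apply the same rule there, or label those rows as the mix of drug classes among treated patients and show them beside EQ1.

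The cost is a sentence of SAP text and, if patients were dropped in the programs, a change of denominator. No new data are needed. Section 5 dates the version 1.0 tables 29 January 2024 and the first abstract 17 February 2024, both before this amendment, so rimegepant rows already produced may need checking and, if affected, re-issue.

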8.5. Study Size

Given the primary research objective is purely descriptive in nature (i.e., no *a priori* hypotheses specified), the available sample size is fixed by the DSP data collection methodology and simply impacts the precision of any estimates. Therefore, formal sample size calculations are not applicable and have not been performed. All patients who meet the eligibility criteria will be included in the study. For this study, the sample size is 528 (91 Rimegepant, 437 Triptans) for the physician-reported outcomes, and 143 (29 Rimegepant, 113 Triptans) for the patient-reported outcomes. Data Management

Pseudoanonymised data are taken from the Migraine VII DSP, which is owned and managed by ARW.

All data analysis will be conducted using Stata 17 software, version 17.0 (StataCorp, College Station, Texas) / IBM® SPSS® Data Collection Survey Reporter v7.5 or the latest available version at time of analysis. All programming code/ syntax written to conduct the required analysis will be logged for transparency and replicability.

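### Section 8.6.3 counts the neutral answer as dissatisfaction for both physicians and patients, so the labelled rate exceeds stated dissatisfaction by exactly the neutral share.

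*Combined protocol and SAP*

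**What the plan says.** Objective 2 is analysed in section 8.6.3. Both satisfaction items, PRF IQ1a (physician) and PSC HQ18a (patient), are first reported category by category: "Proportion of responses to: Extremely satisfied / Satisfied / Slightly Satisfied / Neither satisfied nor dissatisfied / Slightly dissatisfied / Dissatisfied / Extremely dissatisfied". Two derived groups follow, worded identically in the two rows. The first is "Satisfaction will be defined as responses to: 'Extremely satisfied' or 'Satisfied' or 'Slightly Satisfied' combined". The second is "Dissatisfaction will be defined as responses to: 'Neither satisfied nor dissatisfied' or 'Slightly dissatisfied' or 'Dissatisfied' or 'Extremely dissatisfied' combined". Three of the seven answers thus form one group and four form the other, with the midpoint placed in the second.

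Three other places bear on this:

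- The follow-up item to IQ1a is titled "Drivers for lack of satisfaction with current acute treatment (physician perspective"), and HQ18b has the same title from the patient's side.
- The IQ1a row adds "Data to be matched to PSC equivalent data (PSC HQ18a"), and the HQ18a row has the mirror instruction. Neither says what table or statistic the matching is to produce.
- For Objective 3 (section 8.6.4), the 'do not know' answer is omitted and the negative group holds only the two negative answers: "Unwillingness to continue will be defined as responses to 'Probably not' and 'Definitely not' combined".

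Table 1 in section 8.3 lists the seven answers without grouping them. Nothing elsewhere overrides the section 8.6.3 definition or gives a reason for it.

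**The concern.** The name of the derived group contradicts the text of one of the answers in it. Satisfied against everyone else is a legitimate split, but its second half is 'not satisfied', which is wider than 'dissatisfied'.

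Satisfaction is one of the four stated objectives. The amendment adds triptans alongside rimegepant to supply data for a reimbursement submission, and section 11 foresees congress and journal publication. A percentage headed 'Dissatisfaction' can be quoted without the seven-category table beside it. If the neutral share differs between the drugs, or between physicians and patients, the labelled contrast will differ from the contrast in actual dissatisfaction, in a direction that cannot be known beforehand.

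The matched data raise a further point. If the two-way groups are used there, a physician's neutral answer paired with a patient's strongest dissatisfaction counts as agreement that the patient is dissatisfied. The separate category proportions cannot undo that, because they do not show which physician answer went with which patient answer.

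**Working it through.** The plan gives no dissatisfaction rate, so there is no figure to reproduce. The check is an identity applied to the plan's group sizes.

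**Inputs from section 8.5.** Physician-reported: 91 rimegepant and 437 triptans (total 528). Patient-reported: "143 (29 Rimegepant, 113 Triptans) for the patient-reported outcomes". The two patient groups sum to 29 + 113 = 142, not 143; this does not affect the point, since only the group sizes are used.

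**Assumed inputs.** The documents give neither a neutral share nor an explicit dissatisfaction share. The illustrations assume 5–20% neutral and 10–15% explicitly dissatisfied. Complete answers are also assumed, although section 8.6 expects the base to vary by item.

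**Step 1, identity.** Let n be the base, U the number of neutral answers and D the number in the three dissatisfied grades.

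- Rate as planned = (U + D)/n
- Explicit dissatisfaction = D/n
- Difference = U/n, the neutral share, whatever the data

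**Step 2, weight of one neutral answer (1/n).**

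| Source | Group | n | Points added |
|---|---|---|---|
| Patient | Rimegepant | 29 | 3.4 |
| Patient | Triptans | 113 | 0.9 |
| Physician | Rimegepant | 91 | 1.1 |
| Physician | Triptans | 437 | 0.2 |

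**Step 3, illustration at about 10% neutral and 10% explicitly dissatisfied (whole respondents).**

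| Source | Group | U | D | As planned | Explicit |
|---|---|---|---|---|---|
| Physician | Rimegepant | 9 | 9 | 18/91 = 19.8% | 9/91 = 9.9% |
| Physician | Triptans | 44 | 44 | 88/437 = 20.1% | 44/437 = 10.1% |
| Patient | Rimegepant | 3 | 3 | 6/29 = 20.7% | 3/29 = 10.3% |
| Patient | Triptans | 11 | 11 | 22/113 = 19.5% | 11/113 = 9.7% |

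Over the full assumed ranges, the labelled rate runs from 10% + 5% = 15% to 15% + 20% = 35%, where explicit dissatisfaction is 10–15%.

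**Step 4, effect on a contrast.** Suppose neutral answers are 6 of 29 for rimegepant patients and 6 of 113 for triptan patients, with D = 3 and D = 11. The labelled rates are 9/29 = 31.0% and 17/113 = 15.0%, a difference of 16.0 points. Explicit dissatisfaction is 3/29 = 10.3% and 11/113 = 9.7%, a difference of 0.6 points. The counts are invented; they show only that the labelled contrast can come almost entirely from neutral answers.

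**Step 5, the base matters.** The gap equals the neutral share only if neutral answers stay in the denominator, as the plan has it. If they were dropped, the patient rimegepant example of step 3 would give 3/26 = 11.5% against 20.7%, a gap of 9.2 points rather than 3/29 = 10.3.

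**The case against.** The strongest reply is that this is a naming defect, not a distorted estimate. The group's contents are spelled out in both rows. Because the two groups exhaust the scale, 'dissatisfaction' is simply 100% minus the satisfied percentage, and any difference in it is the satisfaction difference with the sign reversed. The explicit rate can be recovered by adding three reported proportions, the analysis is descriptive, and no test or decision uses this group. No concordance statistic is planned, so the harm in the matched data is conditional. The neutral share is unknown, and 1/29 is the weight of any single answer in a group of 29.

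Most of this stands and limits the weight of the point. It does not rescue the label. That the group is the complement of 'satisfied' is why it should not be named as though it measured dissatisfaction. The matched-data concern depends on an output choice that the plan leaves open.

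It can also be said that renaming leaves the neutral and extreme answers in one cell of a matched table. That is true, but 'not satisfied' describes both answers correctly and 'dissatisfied' does not.

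The Objective 3 comparison is imperfect, since 'do not know' is not a scale midpoint. Whether neutral respondents were asked the driver questions cannot be checked, because the questionnaires are not in the available text.

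**Conclusion.** The concern holds. Followed as written, the rule produces a figure headed 'Dissatisfaction' that exceeds explicit dissatisfaction by exactly the neutral share, for both drugs and both perspectives, provided neutral answers stay in the base. The actual size cannot be determined from the documents; the 15–35% range rests wholly on assumed shares. The practical impact is modest for the marginal tables. For the matched physician-patient output it depends on a format that has not been stated. The definition should be corrected, but it does not threaten the study's satisfaction result.

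**What to change.** In both the IQ1a and HQ18a rows of section 8.6.3, do one of the following:

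- **Three groups on one common base:** satisfied (three grades), neutral (the midpoint alone) and dissatisfied (three grades).
- **Keep the two-way split** and rename the second group 'Not satisfied', which agrees with the plan's own title for the driver items.

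Then state that the matched IQ1a/HQ18a output uses the same groups and labels, and what form that output takes.

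The cost is two definitions and a recode or relabel, with no new data. The satisfied percentage and the seven category proportions do not change. The milestones place the Version 1.0 tables (29 January 2024) and the first abstract (17 February 2024) before this version of the plan, with the amended tables one week after it (30 April 2024). Any output already produced under the current label would need relabelling too.
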